9.7.3. Outcome Analysis

Operational definitions for each outcome are described below. Each outcome will be assessed using the primary assessment method for the follow-up period where follow-up will end on the earliest of the following occurrences:

- Disenrollment from health insurance (with a 45-day allowable gap)
- Death
- Discontinuation of voxelotor (with a 45-day allowable treatment gap, voxelotor arm only)
- End of follow-up: up to 1 year from index date (365 days)
- The occurrence of any exclusion criteria events (e.g., pregnancy, stroke, hemodialysis, evidence of HSCT or gene therapy, renal transplant, or liver transplant)

The primary analyses will employ an as-treated follow-up approach that ends follow-up upon treatment changes. Patients will be followed from the index date until treatment change (discontinuation of voxelotor for voxelotor group), or the end of follow-up, whichever is earlier. This as-treated method of analysis allows for an estimate of the effect while the patient is taking the drug of interest and addresses intercurrent events. However, it may introduce bias into the estimates. To adjust for differences in follow-up time between voxelotor patients and their matched controls, matched or pairwise censoring will be applied to censor unexposed on the date of voxelotor discontinuation for their matched pair as a sensitivity analysis.³⁸ A summary of sensitivity analyses is included in Table 7 to evaluate how the magnitude of this bias will be assessed.

Primary Objective - Change in Number of RBC Transfusions PPPY

For each patient, the difference in the number of RBC transfusions PPPY from baseline to follow-up period will be reported as the change and will be calculated as follows:

$$Change = \left(\frac{Number\ of\ RBC\ transfusions\ in\ follow-up}{Available\ days\ of\ follow-up} - \frac{Number\ of\ RBC\ transfusions\ in\ baseline}{365\ days\ *}\right)x\ 365$$

The change in the number of RBC transfusions PPPY will be analyzed using generalized linear model (GLM) with an identity link to estimate the difference in RBC transfusion change rates between the two groups. If any pre-index covariates that are found to be unbalanced after the PS method, it will be included in the regression as a covariate. The rate change and its 95% confidence intervals (CI) will be reported.

For sensitivity analysis, transformations of the outcome may also be considered as appropriate. The outcome data will only be viewed overall prior to selecting a method of regression. 95% CI will be reported for the difference between the groups. Full details will be provided in the SAP.

Exploratory Objective 1 – SCD-related Complications Exploratory Objective 1.1 – Change in SCD-related Complications PPPY

VOCs, ACS, ACS + pneumonia, and priapism will be assessed as the change in the rate of events PPPY from baseline to follow-up. For each individual, the rate of each clinical outcome will be calculated as the number of events divided by the number of person-days. The change will be calculated as:

$$Change = \left(\frac{Number\ of\ events\ in\ follow-up}{Available\ days\ of\ follow-up} - \frac{Number\ of\ events\ in\ baseline}{365\ days\ *}\right)x\ 365$$
*All patients have 365 days of baseline data

The change in number of events PPPY will be analyzed using GLM with an identity link to estimate the difference in clinical outcome change rates between the two groups. If any preindex covariates that are found to be unbalanced after the PS method, it will be included in the regression as a covariate. The rate change and its 95% CI will be reported.

Exploratory Objective 1.2 – Time to Stroke

Stroke will be assessed as a time-to-event outcome. Cox proportional hazards (PH) models will be used to calculate the hazard ratio (HR); 95% CIs will be calculated using a robust variance estimator.

Exploratory Objective 2, Endpoint 1 – Number of RBC Transfusions PPPY in Follow-Up

The number of RBC transfusions that occur during the follow-up period will be assessed PPPY during available follow-up within each group. The mean number of RBC transfusions PPPY will be reported for each group. The mean difference between the groups will be assessed using a GLM similar to the primary analysis. The 95% CI will be reported for the difference between the groups.

Exploratory Objective 2, Endpoint 2 – Proportion of Patients with > 30% Reduction in RBC Transfusions

^{*}All patients have 365 days of baseline data

This outcome will be defined as the proportion of patients with a percent reduction in RBC transfusions between baseline and follow-up that is greater than 30%. For each patient, the percent change will be calculated as follows:

$$Percent Change = \frac{(\frac{Number \ of \ RBC \ transfusions \ in \ follow - up}{Available \ days \ of \ follow - up} - \frac{Number \ of \ RBC \ transfusions \ in \ baseline}{365 \ days \ *} x \ 100}{\frac{Number \ of \ RBC \ transfusions \ in \ baseline}{365 \ days \ *}}$$

*All patients have 365 days of baseline data

The mean percentage change in the number of RBC transfusions PPPY within each group will be reported. The proportion of patients with a 30% reduction in RBC transfusions will also be reported for each group. A logistic regression model will be used to compare the difference of the proportion of patients with the reduction of more than 30% between the groups with an estimated odds ratio. The 95% CIs will also be reported.

Exploratory Objective 2 Endpoint 3 – Proportion of Patients with Zero RBC Transfusions PPPY in Follow-Up

This outcome will be defined as the proportion of patients with zero RBC transfusions PPPY during follow-up. A logistic regression model will be used to compare the percentage of patients without a transfusion in the follow-up time frame between the groups and an odds ratio will be estimated. The 95% CIs will also be reported.

Exploratory Objective 3 – Time to Transfusion-Associated Complications

Each RBC-associated complication (including the composite outcome) will be assessed as a time-to-event outcome. Cox PH models will be used to calculate the HR; 95% CIs will be calculated using a robust variance estimator. The Cox PH regression model may incorporate confounders that remain unbalanced after PS adjustment.

Sensitivity and Subgroup Analyses

Table 7 below includes a summary of the sensitivity analyses and the rationale for performing each analysis. The following sensitivity analyses will be performed for the primary endpoint unless otherwise specified:

Table 7. Planned Sensitivity and Subgroup Analyses

Analysis	Description	Rationale
Intention-to-Treat (ITT)	The follow-up period will be changed from astreated to follow an ITT approach with the exposed group requiring at least one voxelotor claim. All patients will be followed from the index date until disenrollment, death, or end of study period. Follow-up will not end on treatment discontinuation or switches.	To estimate the effect of the "assigned" treatment.

Required 1-year minimum follow-up	Two subgroup analyses have been proposed to evaluate bias introduced by differential follow-up. First, a subgroup analysis of patients with a minimum of 1-year of follow-up will be performed to evaluate the impact of informative censoring.	To address the impact of informative censoring and differential follow-up
Matched censoring	If meaningful differences in follow-up time are observed, matched censoring will be performed to assess the impact of differential follow-up between the exposed and referent group for the primary objective. Bias due to differential follow-up can arise when the reasons for participants dropping out or being lost to follow-up are related to both the treatment and the outcome. Matched censoring mitigates this bias by censoring all patients within a matched set (i.e., patients that have been matched by PS matching) at the earliest time in which a patient in the set was censored. In the context of 1:2 PS matching, where each exposed patient is matched to two referent patients, the matched set will consist of at most three individuals. Thus, matched censoring in this scenario involves censoring data for all three individuals in a matched set at the earliest observed censoring time among them.	To address the impact of informative censoring and differential follow-up
Stratification by number of RBC transfusions in baseline	The number of RBC transfusions PPPY in baseline will be categorized and the primary objective will be reported separately for those categories. This analysis will be performed for all objectives.	To understand the effect of the treatment on high-risk subgroups.
Subgroup analysis by Hb level	The primary analysis will also be performed on a subgroup of patients with Hb values at baseline. A separate PS model will be utilized for this subgroup.	To understand the effect of the treatment on high-risk subgroups and patients with available baseline data.
Subgroup analysis by prior medications	A subgroup analysis will be performed on patients who received hydroxyurea, crizanlizumab, L-glutamine, and/or ESA in baseline the exposed and referent groups.	To understand the effect of other SCD treatments.
Subgroup analysis by concomitant medications	A subgroup analysis will be performed on patients who received hydroxyurea, crizanlizumab, L-glutamine, and/or ESA in baseline the exposed and referent groups. This subgroup analysis will be performed for the Primary Objective and the Exploratory Objective 1 (VOCs).	To understand the effect of other SCD treatments.

Abbreviations: ITT: Intention-to-treat; PPPY: per patient per year; SCD: Sickle cell disease

All subgroup analyses and stratifications must meet a minimum sample size criteria in each group to be performed (see SAP for more detail). Exploratory objective 1 which evaluates the change in the rate of VOCs and its separate components from baseline through follow-up will also include a sensitivity analysis utilizing alternative definitions for VOCs, given a higher likelihood of misclassification in claims using ICD-10 codes alone; these alternative VOC definitions will be detailed in code lists provided in the SAP. Other sensitivity analyses such as e-values may be considered if other possible confounders or sources of bias are identified, depending on effect size in the primary outcome or differences in baseline characteristics and/or follow-up time between the exposed and matched controls. Details on potential sensitivity analyses will be included in the SAP.

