Population: The study population will include individuals with SCD between 12 and 85 years of age who are enrolled in a health insurance plan (commercial, Medicare, Medicaid) continuously during the 365 days prior to and including the index date (baseline) and 180 days post-index. The index selection period will be November 25, 2019 (date of FDA accelerated approval for voxelotor) through January 31, 2023. The exposed group will include patients with a new prescription claim for voxelotor (no use 365 days prior), while the control group will include matched patients who do not have a prescription claim for voxelotor. The exposed group will index on the voxelotor prescription claim date and will be sequentially coarsened-exact-matched with up to four non-voxelotor patients based on age and calendar date. Both the exposed and control groups may be treated with other standard of care (SOC) treatments, such as hydroxyurea, during the study period.

Variables: The exposure of interest will be a voxelotor prescription claim. Baseline characteristics and covariates for PS modeling will include demographic information (e.g., age, sex, insurance type) as well as patient characteristics (e.g., specialty provider type, common SCD comorbidities, treatment history, Hb levels, number of prior RBC transfusions, and healthcare utilization). The primary outcome of interest is RBC transfusion. Exploratory outcomes include VOC, stroke, and RBC transfusion complications. Tables 4 and 5 define exposures, outcomes, and key covariates.

Data sources: The study will use the Komodo Healthcare Map (KHM) database linked to Claritas prescription data (proprietary voxelotor claims) and Quest Diagnostics lab data. Data sources are anchored on a closed system of administrative claims, including patient enrollment, physician, facility, and pharmacy claims.

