9.7.2. Baseline Balance

PS methods will be used to account for baseline balance of covariates between the treated group and matched controls. PS adjustment allows for the inclusion of a pre-defined comprehensive list of confounding covariates to ensure comparable exposure and referent groups, avoiding non-convergent issues of standard outcome models. PS models estimating the ATT will be considered for this analysis. An iterative approach to estimating the PS will be used.

PS Estimation

Potential covariates that affect treatment decisions or outcomes and are eligible for inclusion in the PS model are listed in Table 5.³⁰ Potential confounding covariates will be assessed for balance at baseline using absolute standard differences (ASD). Covariates with an ASD > 0.1 will be considered imbalanced and will be included in a PS model fit using logistic regression. With this approach, the PS will be modeled as the conditional probability of receiving voxelotor given the selected covariates for each individual. The PS modeling will be performed blinded of any outcome to ensure endpoints will not be assessed before a PS method is selected. Diagnostic criteria used to assess PS model estimate are described below and in Table 6. Multiple iterations of the PS model estimation may be performed depending on diagnostic evaluation results.

Use of PS in Baseline Confounder Balance

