The diagnostic results will be presented to the study team who will provide a final confirmation that all the necessary criteria have been satisfied. The inferential analysis phase will only begin after sign-off of the final protocol by the study team, certified by the Principal investigator (PI). More information on the methods used to balance baseline covariates can be found in SAP and in Table 6 below.

Table 6. Diagnostic Checklist

#	Diagnostic	Description	1
1	Confirm positivity of variables	PS distribution will be visually inspected and overlap in all areas of the PS distribution will be confirmed.	
		Additionally, any patients with an observation for covariates not meeting the positivity assumption and may be considered outliers. Further detail on methodology is available in SAP.	
2	Confirm PS model fit	Any covariate with no variability (i.e., a constant value across all observations) will be removed from the PS model. The PS model will be determined as not overfit if each covariate contains ≥ 12 exposed subjects. ³³ Collinear covariates will be defined as any covariates with a Pearson correlation coefficient greater than or equal to 0.7. ³⁴ Collinear variables may be removed from the PS model if large standard errors are observed because including them may lead to biased coefficient estimates. If removed, the model will be refitted. ³⁵	
3	Confirm baseline confounder balance	Balance of all potential confounders (i.e., covariates) will be confirmed for voxelotor vs referent patients. Covariate balance will be defined as an ASD ≤ 0.10. ³⁶ Balance of these variables will still be confirmed after PS matching. Should any variables with small residual imbalance remain, balance may be deemed acceptable if the variable is not a predictor of the outcome among the referent group (defined as an ASD < 0.10 when comparing the risk of the outcome to those with the variable versus those without it). This determination will be made by clinical experts or key opinion leaders on the study team. Evaluation of imbalance in outcome prediction will only be	

1/2	0	23	Dec	am	har	20	124

		conducted once at the end of the diagnostic sub-phase if all other diagnostic criteria are met. Variables with residual imbalance across the exposure and referent groups that are associated with the outcome (e.g., baseline Hb) will be included as an independent variable in the subsequent outcome model.	

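### The primary change-score model should always include the baseline transfusion rate, not only when it fails the balance check: a cheap gain in precision that also closes a small tolerated bias

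*Protocol*

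**What the plan says.** Protocol 9.7.3 defines the primary outcome per patient: "the difference in the number of RBC transfusions PPPY from baseline to follow-up period will be reported as the change". The follow-up rate is annualised over the available days and the baseline rate over 365 days. The model is then fixed: "The change in the number of RBC transfusions PPPY will be analyzed using generalized linear model (GLM) with an identity link". No baseline term is named. Covariates enter by one rule: "If any pre-index covariates that are found to be unbalanced after the PS method, it will be included in the regression as a covariate". The threshold is in Table 6 of 9.7.2: "Covariate balance will be defined as an ASD ≤ 0.10".

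The baseline transfusion count is a candidate for the propensity score (PS). The Abstract lists "Hb levels, number of prior RBC transfusions, and healthcare utilization" among the PS covariates, and Table 4 gives RBC transfusion a covariate role. Entry to the PS model is itself conditional under 9.7.2: "Covariates with an ASD > 0.1 will be considered imbalanced and will be included in a PS model fit using logistic regression". Table 6 adds that for a small residual imbalance "balance may be deemed acceptable if the variable is not a predictor of the outcome among the referent group", and that imbalanced variables associated with the outcome go into the outcome model.

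The Abstract (Data analysis) makes inclusion of unbalanced covariates optional, whereas 9.7.3 makes it mandatory.

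Exploratory Objective 1.1 (VOC, ACS, priapism) copies the primary approach: "The change in number of events PPPY will be analyzed using GLM with an identity link", with the same conditional rule.

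**The concern.** Change is follow-up minus baseline, so it depends on baseline unless the regression slope of follow-up on baseline is exactly 1. Leaving baseline out has two consequences.

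- **Precision.** Variation in change that baseline would explain stays in the error term, even when the arms' baseline means match perfectly.
- **Bias from tolerated imbalance.** A baseline gap at or below ASD 0.10 counts as balance and is not adjusted for. If the slope differs from 1, part of that gap passes into the treatment contrast.

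For Objective 1.1 the conditional rule has less to act on. Table 4 and Annex Table 1 carry VOC, ACS and priapism as presence of a code, summarised as number and percent. An imbalance in baseline event counts might therefore never show up in the balance check.

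**Working it through.** **Inputs from the protocol (9.5):** SD of change 3.0, target difference 1 transfusion PPPY, 185 treated and 370 controls, variance factor 1.65, power 80%. Alpha is not stated in 9.5; two-sided 0.05 is assumed from the 95% intervals.

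**Inputs not in the protocol:** the baseline/follow-up correlation r, and the ratio q of follow-up SD to baseline SD. A q above 1 is plausible because follow-up may be annualised from about 180 days, whereas baseline is always 365. I take r = 0.3 to 0.9 and q = 1 to 1.5.

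**Step 1: the plan's own figure.** SE = 3.0 × √(1.65 × (1/185 + 1/370)) = 0.347. Power = Φ(1/0.347 − 1.96) = 82% (82.0% with a t-test). Solving for N: 1.5 × 9 × (1.960 + 0.842)² = 106 treated, and × 1.65 gives 175, against 185 stated. The stated size is slightly conservative.

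**Step 2: formulas.** Let s be the baseline SD and β = rq the common slope.
- Var(change) = s²(1 + q² − 2rq) = 9, which fixes s.
- Residual variance with baseline in the model = q²s²(1 − r²).
- Variance ratio = q²(1 − r²)/(1 + q² − 2rq) = 1 − (1 − rq)²/(1 + q² − 2rq). It never exceeds 1, and equals 1 only when the slope is 1. For q = 1 it reduces to (1 + r)/2.
- A baseline gap δ shifts the unadjusted contrast by (β − 1)δ. At ASD 0.10, δ = 0.10s, so the size is 0.10 × s × |1 − rq|.

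**Step 3: results, holding the SD of change at 3.0 and applying the factor 1.65 to both models.**

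| q | r | Slope | Variance ratio | Power, adjusted | Size of bias at ASD 0.10 |
|---|---|---|---|---|---|
| 1 | 0.3 | 0.30 | 0.65 | 95% | 0.18 |
| 1 | 0.5 | 0.50 | 0.75 | 91% | 0.15 |
| 1 | 0.7 | 0.70 | 0.85 | 88% | 0.12 |
| 1 | 0.9 | 0.90 | 0.95 | 84% | 0.07 |
| 1.25 | 0.3 | 0.38 | 0.78 | 90% | 0.14 |
| 1.25 | 0.5 | 0.63 | 0.89 | 86% | 0.10 |
| 1.25 | 0.7 | 0.88 | 0.98 | 83% | 0.04 |
| 1.25 | 0.9 | 1.13 | 0.95 | 84% | 0.07 (reversed) |
| 1.5 | 0.3 | 0.45 | 0.87 | 87% | 0.11 |
| 1.5 | 0.5 | 0.75 | 0.96 | 84% | 0.06 |
| 1.5 | 0.7 | 1.05 | 1.00 | 82% | 0.01 (reversed) |
| 1.5 | 0.9 | 1.35 | 0.78 | 90% | 0.14 (reversed) |

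Worked row (q = 1, r = 0.5): s = 3.0; residual SD = 3.0 × √0.75 = 2.60; SE = 2.60 × 0.1157 = 0.3005; power = Φ(1/0.3005 − 1.96) = 91%; bias = 0.10 × 3.0 × 0.5 = 0.15.

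Reversed means that the slope exceeds 1, so the same baseline gap pushes the estimate the other way. The largest bias, 0.18, is 18% of the 1-unit target and about half a standard error (0.177/0.347 = 0.51).

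**Step 4: count-data check.** A gamma-Poisson simulation with at least 2 baseline transfusions, follow-up of 180 to 365 days and assumed mean rates of 3 to 6 gave slopes of 0.52 to 0.88, variance ratios of 0.68 to 0.96 and bias at ASD 0.10 of 0.08 to 0.28. The 0.28 came with an SD of change of 4.91; rescaled to the planning SD it is 0.278 × 3.0/4.91 = 0.17, within the table's range.

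**The case against.** Much of the opposing case stands.

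- **Regression to the mean.** A reader might infer that requiring at least 2 baseline transfusions biases the comparison in itself. It does not: the requirement applies to both arms, and the shared part cancels in the difference. Only the part tied to residual baseline imbalance remains.
- **Expected bias.** A reader might take 0.18 as a forecast, or as favouring voxelotor. Prior transfusions are a PS candidate, matching uses a caliper, and balance is rechecked afterwards. The achieved ASD may be well below 0.10, and the sign depends on which arm starts higher and on the slope.
- **Power.** A reader might infer that the study is underpowered. It is not: the plan delivers about 82% against 80% stated.
- **Size of the gain.** The equal-SD rows flatter it. With annualised short follow-up the gain can be close to nil.
- **Existing safeguards.** Table 6 sends imbalanced, outcome-associated variables into the model, and Table 7 stratifies by baseline transfusions for all objectives. Neither adjusts the primary estimate when the ASD is 0.10 or less.
- **Estimand.** If the effect varies with baseline, a single adjusted coefficient may differ slightly from the average effect in the treated that the protocol targets.
- **Objective 1.1.** It is exploratory, and the continuous visit count in Table 4 partly carries event frequency.

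Details of model selection are left to an SAP that is not shown, so an additional adjusted model may exist there. But the outcome scale and the conditional rule are stated in the protocol, and section 9.7 says that major changes to primary endpoint analyses would be reflected in an amendment.

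**Conclusion.** The point holds as a cheap improvement, not as an error in the stated power. The protocol makes adjustment for the baseline transfusion rate depend on an ASD threshold, although that rate is one of the two terms of the outcome. Under a common slope, fixing it in the model is asymptotically never less precise and removes the bias linked to tolerated imbalance.

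At the planning SD of 3.0, and over the assumed r and q, the variance reduction is about 0 to 35%, power is about 82 to 95%, and the bias ceiling at ASD 0.10 is about 0.18 transfusions PPPY in either direction. The direction of the argument is firm; the figures are conditional, because neither r nor q is in the protocol. Adjustment does not address unmeasured confounding, or regression toward different underlying means in the two arms.

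**What to change.** In 9.7.3, state that baseline RBC transfusions PPPY is always a term in the primary model whatever its ASD, and that the baseline count of the same event is always a term in each Objective 1.1 model. Keep the unadjusted change score as a sensitivity analysis. Reconcile the Abstract, where including unbalanced covariates is optional, with 9.7.3, where it is mandatory.

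The cost is a few sentences in the protocol, matching text in the SAP and one more reported sensitivity analysis. No new data are needed, because every patient has 365 baseline days. The small downside is the possible departure of the adjusted coefficient from the average effect in the treated if the effect varies with baseline; the planned stratification by baseline transfusions would help to show whether it does.

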9.2.1. Inclusion Criteria

Table 2. Summary of Inclusion Criteria

Inclusion Criteria	Assessment Period	Operational Definition	Rationale/Validated Source
Confirmed diagnosis of SCD	[Baseline]	1 inpatient medical claim with an International Classification of Diseases (ICD), Tenth Revision, Clinical Modification (ICD-10-CM) diagnosis code for SCD or 2 outpatient claims with an ICD-10-CM diagnosis code for SCD at least 30 days apart (including all genotypes as well as unknown type)	Administrative claims study ²⁰
Age between 12 and 85 years	[Index]	Age in years since year of birth	Age range covers the initial accelerated approval indication.
≥ 2 RBC transfusions	[Baseline]	At least 2 medical claims with an ICD Tenth Revision, Procedure Coding System (ICD-10-PCS) procedure code for an RBC transfusion at least 1 day apart (maximum 1 transfusion counted per day).	The subset of SCD patients who would most benefit from a reduction in RBC transfusion and necessary to measure a change from baseline to follow-up.
≥ 365 days of continuous enrollment during baseline and at least 180 days in follow up	[Baseline] [Follow Up	Both medical and pharmacy enrollment is required for observability (with a 45-day allowable gap between claims).	Observability is required to assess whether outcomes occurred and were not assumed to be missing.
≥ 180 days of continuous voxelotor use post-index (with 45-day gaps allowed) – voxelotor arm only	[Follow up]	At least 180 days of continuous voxelotor use post-index (with 45-day gaps allowed) defined using the voxelotor ship date and days supply reported on the claim— voxelotor arm only	Adequate exposure to voxelotor is necessary to evaluate the impact on RBC transfusions and other outcomes.

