Table 5. Description of Endpoints and Alignment to Study Objectives

Endpoint	Assessment Period	Output	Objective Alignment
Change in RBC transfusions	[Baseline]; [Follow-up]	Mean change in the number of RBC transfusions (maximum 1 per day) PPPY from baseline to follow-up	Primary Objective
VOCs	[Baseline]; [Follow-up]	Mean change in the number of events (maximum 1 per day) PPPY from baseline to follow-up. VOC events need to occur more than 5 days apart to be considered separate events.	Exploratory Objective 1.1
ACS	[Baseline]; [Follow-up]	Mean change in the number of events (maximum 1 per day) PPPY from baseline to follow-up	Exploratory Objective 1.1
ACS Including Pneumonia	[Baseline]; [Follow-up]	Mean change in the number of events (maximum 1 per day) PPPY from baseline to follow-up	Exploratory Objective 1.1
Priapism	[Baseline]; [Follow-up]	Mean change in the number of events (maximum 1 per day) PPPY from baseline to follow-up	Exploratory Objective 1.1

Voxelotor

V2.0 23 December 2024		9	
Stroke (including transient ischemic attack)	[Follow-up]	Time to event during follow-up	Exploratory Objective 1.2
RBC transfusions in follow-up	[Follow-up]	Mean number of RBC transfusions (maximum 1 per day) PPPY in follow-up	Exploratory Objective 2
Percent reduction in RBC transfusion > 30%	[Baseline]; [Follow-up]	Proportion of patients with a percentage decrease in the number of RBC transfusions (maximum 1 per day) PPPY from baseline to follow-up that is greater than 30%	Exploratory Objective 2
Zero RBC transfusions in follow-up	[Follow-up]	Proportion of patients with 0 RBC transfusions (maximum 1 per day) PPPY during follow- up	Exploratory Objective 2
Iron overload	[Follow-up]	Time to event during follow-up	Exploratory Objective 3
Iron chelation use	[Follow-up]	Time to event during follow-up	Exploratory Objective 3
Delayed hemolytic transfusion reactions	[Follow-up]	Time to event during follow-up	Exploratory Objective 3
Alloimmunization	[Follow-up]	Time to event during follow-up	Exploratory Objective 3
Composite outcome (iron overload, iron chelation use, delayed hemolytic transfusion reactions, and/or alloimmunization)	[Follow-up]	Time to event during follow-up	Exploratory Objective 3

Abbreviations: ACS: Acute Chest Syndrome; PPPY: per patient per year; RBC: Red blood cell; VOC: vaso-occlusive crisis The table above includes a summary of the outcomes of interest for this analysis. Operational definitions can be found in the data analysis plan (Section 9.7).

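### The zero-transfusion endpoint is compared by logistic regression that ignores observation time, although drug discontinuation ends follow-up in the voxelotor arm only

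*Protocol*

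**What the plan says.** Section 9.7.3 defines Endpoint 3 of Exploratory Objective 2 as the proportion of patients with zero RBC transfusions PPPY in follow-up. The comparison is set out in one sentence, "A logistic regression model will be used to compare the percentage of patients without a transfusion in the follow-up time frame between the groups", and is summarised by an odds ratio with a 95% CI.

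The same section lists what ends follow-up for every outcome. One item applies to one arm: "Discontinuation of voxelotor (with a 45-day allowable treatment gap, voxelotor arm only". The cap is "End of follow-up: up to 1 year from index date (365 days". Disenrollment, death and the occurrence of an exclusion event end follow-up in both arms.

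Table 2 (section 9.2.1) sets the lower limits. The voxelotor arm needs "At least 180 days of continuous voxelotor use post-index (with 45-day gaps allowed"; both arms need "365 days of continuous enrollment during baseline and at least 180 days in follow up".

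Sections 9.7.3 and 9.9 acknowledge that as-treated censoring can bias the comparison. The text before Table 7 applies the listed sensitivity analyses to the primary endpoint unless otherwise specified. The matched-censoring row states its purpose as to "assess the impact of differential follow-up between the exposed and referent group for the primary objective", and makes the analysis conditional on a meaningful difference in follow-up. Only the stratification by baseline transfusions is extended to all objectives.

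**The concern.** Whether a patient has zero events depends on how long the patient is observed. Writing the endpoint as zero PPPY does not remove this, because zero divided by any number of days is zero. The voxelotor arm has an additional stopping rule that the controls lack, so its observation time tends to be shorter, by at most 365 − 180 = 185 days for a patient who discontinues. The logistic model then attributes to the drug a difference that comes from the length of the window.

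The main follow-up checks are not directed at this endpoint. In the null simulations below, unequal follow-up left the mean change in PPPY unaffected (difference about 0.00), so Table 7 directs matched censoring at an outcome that this mechanism does not bias. The stroke and transfusion-complication endpoints use Cox models, which account for observation time. The zero endpoint does not. At stake is an exploratory odds ratio in reports that section 12 says are planned for FDA and EMA.

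**Working it through.** The protocol states no figure for this endpoint, so there is none to reproduce. The check asks what odds ratio (OR) the planned comparison gives when the true transfusion rate is the same in both arms.

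**From the protocol:** discontinuation censoring in the voxelotor arm only, falling between about day 180 and day 365; at least 2 baseline transfusions; 185 voxelotor patients and 370 controls (section 9.5).

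**Assumed, because the protocol gives no value:** transfusion rates, their spread between patients, the share of voxelotor patients stopping between days 180 and 365, and stopping that is uniform over those days and unrelated to the transfusion rate.

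**Step 1, closed form.** Take rate r = 2 per year, controls seen for the full year, and half of voxelotor patients stopping uniformly over t = 180/365 = 0.493 to 1 year.

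- Same rate for every patient (Poisson), P(0 | t) = exp(−rt):
  - Controls: exp(−2) = 0.135.
  - Stoppers: [exp(−0.986) − exp(−2)] / (2 × 0.507) = (0.373 − 0.135)/1.014 = 0.234.
  - Voxelotor arm: 0.5 × 0.135 + 0.5 × 0.234 = 0.185.
  - OR = (0.185/0.815)/(0.135/0.865) = 1.45.
- Gamma-distributed rates, shape 2, P(0 | t) = (1 + rt/2)^−2:
  - Controls: 0.250.
  - Stoppers: (1/1.493 − 1/2)/0.507 = 0.335.
  - Voxelotor arm: 0.292.
  - OR = (0.292/0.708)/(0.250/0.750) = 1.24.

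Variation between patients reduces the bias but does not remove it.

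**Step 2, simulation with the eligibility rule.** Patient rates are gamma with shape 1 and mean 2, 4 or 8 per year before requiring at least 2 baseline transfusions, so the selected patients' mean is higher. In addition, 10% of controls are censored uniformly over days 180 to 365. Mean follow-up is 356 days in controls, against 342, 319 and 296 days in the voxelotor arm for the three stopping shares.

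| Voxelotor patients stopping, days 180–365 | Null OR (mean rate 2 / 4 / 8) | Chance of a significant result favouring voxelotor, 185 v 370 |
|---|---|---|
| 25% | 1.10 / 1.09 / 1.11 | 4–6% |
| 50% | 1.24 / 1.28 / 1.33 | 10–13% |
| 75% | 1.40 / 1.47 / 1.51 | 17–28% |

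The nominal chance in that direction is 2.5%, taking two-sided 5% from the 95% CIs.

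**Step 3, same scenarios with remedies.** A common 180-day window gives null ORs of 0.99 to 1.01. Censoring both members of a matched pair at the earlier time gives 0.98 to 1.01.

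**The case against.** The strongest reply is that the protocol sees the problem and has acted on it. The 180-day use and enrollment requirements limit the gap, follow-up time is to be described by arm before outcomes are assessed, and controls are censored too. Section 9.7.3 introduces matched censoring in general text placed before any objective, and section 9.9 does not restrict it either. The text after Table 7 allows further sensitivity analyses if follow-up differs, with details left to the SAP. Table 4 lists follow-up time among possible covariates. The endpoint is exploratory.

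Part of this stands. The 180-day rule makes the bias moderate. Null ORs of 3.8 (2 per year) to 8.7 (4 per year) arise only if every voxelotor patient stops at day 180, every control is seen for 365 days and all patients share one rate; nothing in the protocol supports that. The matched-censoring wording can be read more widely than Table 7, but Table 7 is specific and names the primary objective. Table 4 offers follow-up time as a possible propensity-score covariate, not as a term in this model. The model, effect measure and scope of the sensitivity analyses are stated choices, not details left open.

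A reader might infer that Endpoint 2 of the same objective is biased toward voxelotor as well, since "A logistic regression model will be used to compare the difference of the proportion of patients with the reduction of more than 30"% also names no time term. The documents do not support that. The endpoint is the "Proportion of patients with a percentage decrease in the number of RBC transfusions (maximum 1 per day) PPPY from baseline to follow-up", so it is built from annualised rates. A shorter window adds noise to each patient's rate, and the effect on the proportion past the cut-off depends on where the typical change lies. In the Step 2 scenarios its null OR was 0.99 to 1.07. Over a wider grid it ran from 0.68 (follow-up rate half of baseline, all stopping at day 180) to 1.85 (follow-up rate 1.2 times baseline, all stopping at day 180). The direction is not fixed.

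**Conclusion.** The point holds for the zero-transfusion endpoint. As planned, its odds ratio favours voxelotor in the absence of any effect whenever voxelotor follow-up is shorter and stopping is unrelated to the transfusion rate. The direction follows from the arm-specific censoring rule. The size depends on assumed rates and stopping shares: a null OR of about 1.1 with 25% stopping, 1.2 to 1.3 with 50%, and 1.4 to 1.5 with 75%. It does not extend to the primary mean change, nor as a directional bias to the endpoint of more than 30% reduction. Because the endpoint is exploratory, this should be corrected but does not undermine the primary analysis.

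**What to change.** Any one of three changes to Endpoint 3 is enough:

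- Evaluate zero transfusions over days 1 to 180 in both arms and keep the logistic model. The enrollment and use requirements largely guarantee this window. A rule is needed for the few patients censored earlier by an exclusion event. This option also works if weighting replaces matching under section 9.7.2.
- Apply matched censoring to this endpoint. This depends on matched sets being retained.
- Analyse time to first transfusion with the Cox approach already planned for stroke and transfusion complications.

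In addition, extend the follow-up sensitivity analyses in Table 7 to Exploratory Objective 2. Including the endpoint of more than 30% reduction is reasonable, because its classification also depends on window length.

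A complementary log-log model with log follow-up time as offset is not a safe substitute, because it assumes one constant rate. With gamma shape 1 and 2 per year, P(0) is 0.503 at 180 days and 0.333 at 365 days. The null hazard ratio is then (0.686/0.493)/1.099 = 1.27, against voxelotor.

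The cost is one changed definition or model. The fixed window ignores transfusions after day 180 for this one exploratory endpoint.
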